# 2 LAY SUMMARY

This is a study of a new vaccine against Crimean-Congo haemorrhagic fever (CCHF) virus in healthy adults.

CCHF is a potentially fatal viral illness spread by ticks, which can live on many wild and domestic animals, including cattle, sheep and goats. Humans usually acquire CCHF infection following a tick bite, although it can also be acquired from contact with blood or tissues from infected animals or humans. Infection may be asymptomatic, but it can cause severe disease with impaired blood clotting leading to serious bleeding and death. The disease occurs over a wide geographical area including southern Europe, Africa, south-east Asia and the Middle East. According to World Health Organisation estimates, 3 billion people are at risk from CCHF, and there are 10,000 to 15,000 cases each year, resulting in 500 deaths.

The study vaccine is called ChAdOx2 CCHF. It has been developed by the University of Oxford, using similar technology to the Oxford/AstraZeneca COVID-19 vaccine. This study will be the first to give this vaccine to humans. Its purpose is to assess the tolerability and safety of the vaccine and to measure immune responses after vaccination. The study will also investigate whether having received other similar (adenovirus based) vaccines in the past affects the response to ChAdOx2 CCHF.

We plan to recruit 46 people aged between 18 and 55 years. Volunteers will be screened for eligibility with an initial online questionnaire followed by an in-person medical assessment. Eligible participants will be invited to attend the first vaccination visit. A second vaccination will be given approximately 12 weeks later. Participants will record symptoms after each vaccination in an e-diary. Blood tests will be taken to assess response to the vaccinations. Adverse events will be recorded throughout the trial and participants will be followed up for 1 year.

REC Ref: <rec ref=""></rec> IRAS project ID: 100  Protocol V2.0, 14 th June 2	Crimpan-Congo Haemorrhagic Eever (a lite-	Page 6 of 78

# 3 SYNOPSIS

	-
Trial Title	A phase I safety and immunogenicity study of a CCHF virus vaccine, ChAdOx2 CCHF, in healthy volunteers aged 18 to 55 in the UK
Trial Sites	Site 1: Oxford Vaccine Group Centre for Clinical Vaccinology and Tropical Medicine (CCVTM) Churchill Hospital, Oxford
	Site 2: University Hospital Southampton NHS Foundation Trust [name] Southampton [name]
	Site 3 – non-recruiting: Oxford University Hospitals Foundation Trust [name], Headington, Oxford [name]
Funder	UK Research and Innovation
Trial Code	CCHF01
Study Design	First-in-human, multi-centre, open-label phase I clinical trial with an initial lead-in cohort (Cohort 1)
Vaccine Schedule	2 doses, given at 0 weeks and 12 weeks
Population	Healthy adults aged 18 to 55 years, with or without previous exposure to an adenoviral-vectored vaccine
Planned Sample Size	46 participants (6 in Cohort 1; 40 in Cohort 2)
Follow-up Duration	12 months (from the first vaccination)
Primary Objective	To assess the safety and tolerability of ChAdOx2 CCHF in healthy adult volunteers
Secondary Objective	To assess the immunogenicity of ChAdOx2 CCHF in healthy adult volunteers
Investigational Product	ChAdOx2 CCHF (5 $\times$ 10  viral particles (vp) per dose administration)
Route	Intramuscularly (IM) into the deltoid region of the arm

Cohort	Group	Number of participants	Age (years)	Previous ChAdOx vaccine	Intervention 1 (D0)	Intervention 2 (D84)	Follow-up
1		6	18-55	Either Yes or No	5x10  vp	5x10  vp	1 year

REC Ref: <rec ref=""> IRAS project ID: 1007128 Protocol V2.0, 14th June 2023</rec>	Crimean-Congo Haemorrhagic Eever (a lite-	Page 7 of 78
---	---	--------------

					ChAdOx2 CCHF	ChAdOx2 CCHF	
	А	20	18-55	Yes	5x10  vp	5x10  vp	1 year
2					ChAdOx2 CCHF	ChAdOx2 CCHF	
2	В	20	18-55	No	5x10  vp	5x10  vp	1 year
					ChAdOx2 CCHF	ChAdOx2 CCHF	

#### 4 SCHEDULE OF PROCEDURES TABLES

#### 4.1 Schedule of procedures table: Screening visit (all volunteers)

**Table 1** Schedule of procedures: Screening Visit (all volunteers)

Visit Number	S
Visit type	Screening
Timeline 	7 to 90 days before D0
Visit Procedures	
Informed consent	Х
Review inclusion and exclusion criteria	Х
Record demographic data	Х
Medical history 	Х
Vital signs (heart rate, temperature, blood pressure)	Х
Screening physical examination	Х
TOPS registration	Х
www.tops.org.uk	
Urine Samples	
High-sensitivity Urinary HCG (POCBP only)	Х
Stool Samples (Optional)*	
Sample containers and instructions provided	(X)*
Blood Samples 	
HBsAg, HCV Ab, HIV serology (mL)	~5
Biochemistry, haematology (mL)	~5
Blood volume per visit (mL)	~10
Cumulative blood volume (mL)	~10

Additional unscheduled screening visits may occur (for example: to repeat a blood test, for safety or where clinically indicated)

Medical history may be initially assessed by a telephone call prior to screening (see section 9.2); information obtained in this way will be reviewed at the screening visit

Minor differences in blood volumes may occur depending on the collection tubes and equipment used (~ = approximately); additional repeat blood draws may be required (for example, if there is a problem with the sample or result abnormality)

\* For Cohort 2 participants only

() = optional

#### 4.2 Schedule of procedures table: Vaccination and follow up visits (Cohort 1)

Table 2 Schedule of procedures: Vaccination and follow up visits (Cohort 1)

REC Ref: <rec ref=""> IRAS project ID: 1007128 Protocol V2.0, 14th June 2023</rec>	CCHF01: A study of a new vaccine against Crimean-Congo Haemorrhagic Fever (a life- threatening tick-borne viral disease)	Page 8 of 78
---	--	--------------

Visit Number	1	2	3	4	5	6	7	8	9	10	11	12	13	14
Visit type	Vac1	f/u	f/u	f/u	f/u	f/u	Vac2	f/u	f/u	f/u	f/u	f/u	f/u	f/u
Timeline 	D0	D2	D7	D14	D28	D56	V2 D84	V2 +2	V2 +7	V2 +14	V2 +28	V2 +56	V2 +140	V2 +280
Time window (days)		±1	±3	±3	±3	±7	±14	±1	±3	±3	±3	±7	±28	±60
Visit Procedures														
Review contraindications, inclusion and exclusion criteria	х						х							
Vaccination	Х						Х							
Vital signs (heart rate, temperature, blood pressure)	х	х	x	x	x	x	х	х	x	x	x	x	x	x
Targeted medical history/physical examination, if required 	(X)	(X)	(X)	(X)	(X)	(X)	(X)	(X)	(X)	(X)	(X)	(X)	(X)	(X)
Adverse Event														
Collection														
Solicited AE collection	D	0 to D7	7				V2	to V2+	.7					
Unsolicited AE collection		D	0 to D2	28				V2	to V2+	28				
SAEs & AESI collection	х	х	х	х	х	х	х	х	х	х	х	х	х	х
Review ongoing AEs		х	х	х	х	х	х	х	х	х	х	х	х	х
Electronic diary (eDiary) 														
Electronic diary started	х						х							
Electronic diary review (in clinic)		х	х	х	х			х	х	х	х			
Electronic diary closed					х						х			
Urine Samples														
High-sensitivity Urinary hCG (POCBP only)	х						х							х

Visit Number 1	2	3	4	5	6	7	8	9	10	11	12	13	14

REC Ref: <rec ref=""> IRAS project ID: 1007128 Protocol V2.0, 14th June 2023</rec>	CCHF01: A study of a new vaccine against Crimean-Congo Haemorrhagic Fever (a life- threatening tick-borne viral disease)	Page 9 of 78
---	--	--------------

Visit type	Vac1	f/u	f/u	f/u	f/u	f/u	Vac2	f/u	f/u	f/u	f/u	f/u	f/u	f/u
Timeline 	D0	D2	D7	D14	D28	D56	V2 D84	V2 +2	V2 +7	V2 +14	V2 +28	V2 +56	V2 +140	V2 +280
Time window (days)		±1	±3	±3	±3	±7	±14	±1	±3	±3	±3	±7	±28	±60
Blood Samples 														
HLA typing (mL)	~4													
Biochemistry, Haematology (mL) [LFTs U+Es, FBC]	~5	~5	~5	~5	~5	~5	~5	~5	~5	~5	~5	~5	~5	~5
Immunology (mL)	~50			~50	~50	~50	~50			~50	~70	~50	~50	~50
Blood volume per visit (mL)	~59	~5	~5	~55	~55	~55	~55	~5	~5	~55	~75	~55	~55	~55
Cumulative blood volume (mL)	69	74	79	134	189	244	299	304	309	364	439	494	549	604

Additional unscheduled visits may occur (for example: to repeat a blood test, for additional clinical review)

eDiaries are remotely monitored in (near) real-time for the occurrence of grade  $\geq$ 3 AEs and daily for non-completion

Minor differences in blood volumes may occur depending on the collection tubes and equipment used (~ = approximately); additional repeat blood draws may be required (for example: if there is a problem with the sample, abnormality in the results, or participant unwell)

 optional, at the discretion of the investigator

REC Ref: <rec ref=""> IRAS project ID: 1007128 Protocol V2.0, 14th June 2023</rec>	CCHF01: A study of a new vaccine against Crimean-Congo Haemorrhagic Fever (a life- threatening tick-borne viral disease)	Page 10 of 78
---	--	---------------

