## 9.5.2 Follow-up visits

Vaccination visits are held at the study site (or remotely, if required, see section 9.5.4). Follow-up visits may require the following procedures:

- Review of AEs/AESIs/SAEs, as appropriate, since the last visit
- Review eDiary entries and laboratory blood tests
- Record oral temperature, pulse and blood pressure
- Perform blood draw
- For cohort 2 only, optional collection of stool sample and supply 'By Post' stool collection kit, as required
- Schedule next visit and re-iterate participant requirements such as eDiary entries
- A high-sensitivity urine pregnancy test will be performed at the final visit for all participants of childbearing potential.

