## 11.6 Procedures for collecting and recording Adverse Events

Abnormal clinical findings from medical history, examination or blood tests will be assessed by a delegated clinician / Investigator to determine clinical significance.

All AEs that are observed by the Investigator or reported by the participant, irrespective of their relatedness to the study vaccination, will be recorded from the day of vaccination and until 28 days after each vaccination. These will be either recorded by the participants in the e-diary and/or in the eCRF. Outside of this window (i.e. from 28 days after each vaccination and until the point of a subsequent vaccination or until the final visit if vaccination course completed), non-serious AEs will only be recorded if they require medical attention (contact with GP, visit to emergency department). These will be recorded in the eCRF by the study team.

Type of AE	Study period	eDiary	eCRF
Solicited	Day 0-7	х	
Unsolicited	Day 0-7	х	х
	Day 8-28 post each vaccine dose	х	х
Chonened	Day 28-end of study (medically attended AEs only)		х

**Table 9:** Recording of solicited and unsolicited adverse events

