## **11.8 Unsolicited Adverse Events**

Unsolicited adverse events, *i.e.* those collected through open questioning (*e.g.* "did you experience any new illnesses?"), that are not solicited adverse events and do not constitute SAEs or AESIs, will be collected from the day IMP is administered to the end of the study as follows:

- Day 0 day 28 post each vaccine: These will be recorded in the participant's eDiary and/or ecRF. All reported events will be reviewed at clinic visits and transferred to relevant eCRF on the clinical database if necessary.
- Day 28 to subsequent vaccination or until the final visit (if vaccination course completed) only non-serious medically attended AEs that occur from the time of vaccination to the end of the study will be recorded in the relevant eCRF on the clinical database.

Severity will be self-assessed by participants according to severity grading scales provided to them. Causality will be assigned by the PI-delegated clinician / Investigator as per section 11.3.

If clarification of any event is required, then the study nurse or doctor will seek this from the participant during a clinic visit or by telephone call.

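### eDiary closure is tied to the D28 and V2+28 visits (±3 days), so prospective diary capture of unsolicited AEs can stop up to 3 days short of the stated day-28 period

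*Protocol*

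**What the plan says.** In sections 4.2 and 4.3 (Tables 2 and 3) the row "Electronic diary closed" is marked under the D28 and V2+28 visits in both cohorts. Those visits have a window of 3 days either side. In the same tables the row "Unsolicited AE collection" runs from D0 to D28 and from V2 to V2+28.

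Section 11.6 says that all AEs "will be recorded from the day of vaccination and until 28 days after each vaccination". On the route it says: "These will be either recorded by the participants in the e-diary and/or in the eCRF". Table 9 in that section ticks both the eDiary and the eCRF for unsolicited AEs on days 8 to 28. Outside that period, "non-serious AEs will only be recorded if they require medical attention".

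Section 11.8 gives the same two routes and adds: "All reported events will be reviewed at clinic visits and transferred to relevant eCRF on the clinical database if necessary". Section 9.5.2 lists, among the follow-up visit procedures, "Review of AEs/AESIs/SAEs, as appropriate, since the last visit", and section 9.5.1 has a similar item for the second vaccination visit. Section 9.6 describes the diary but gives no closing date. Section 6.1 makes the occurrence of unsolicited AEs primary outcome (c).

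**The concern.** The recording period is defined by days since vaccination, whereas diary closure is attached to a visit that may take place before the period ends. A participant seen on D25 whose diary is closed that day has no open diary on D26, D27 and D28, although Table 9 counts the eDiary as a route on those days.

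The length of prospective capture for a primary safety outcome would then vary with appointment date. A late visit does no harm, because entries with onset after D28 can be set aside by date. An early visit leaves days that cannot be recovered from the diary. Closure also ends the near real-time remote monitoring for grade 3 or higher events and the daily check for non-completion, both described in footnote 2 to Tables 2 and 3.

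**Working it through.** This is calendar arithmetic on the schedule. No power or sample-size figure is involved.

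**Inputs**
- Closure visits: D28 ±3 and V2+28 ±3, both cohorts (Tables 2 and 3).
- Stated period: D0 to D28 and V2 to V2+28 (Tables 2 and 3; section 11.6), which is 29 calendar days counting day 0.
- Next scheduled visit in Cohort 1: D56 ±7 after dose 1 and V2+56 ±7 after dose 2 (Table 2).
- Next scheduled visit in Cohort 2: V2 at D84 ±14 after dose 1 and V2+140 ±28 after dose 2 (Table 3).

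**Diary days at risk**
- Earliest closure: 28 − 3 = D25 (V2+25).
- Days without an open diary: D26, D27, D28, so 3 of 29 = 10.3% per dose, and 6 of 58 over two doses.
- Visit on D28 or later: 0 days.

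**Interval from closure on D25 (V2+25) to the next scheduled visit**

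| Cohort, dose | Next visit can fall on | Days after closure |
|---|---|---|
| 1, dose 1 | D49 to D63 | 49 − 25 = 24 to 63 − 25 = 38 |
| 1, dose 2 | V2+49 to V2+63 | 24 to 38 |
| 2, dose 1 | D70 to D98 | 70 − 25 = 45 to 98 − 25 = 73 |
| 2, dose 2 | V2+112 to V2+168 | 112 − 25 = 87 to 168 − 25 = 143 |

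Cohort 2 is 40 of the 46 participants. If everyone receives both doses, 80 of 92 dose windows carry the longer intervals.

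**Range over the trial**

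The protocol gives no distribution of visit dates. With 92 dose windows there are 92 × 29 = 2,668 calendar days.
- All visits on D28 or later: 0 days without a diary.
- Visits spread evenly over D25 to D31 (an assumption, for illustration only): the losses are 3, 2, 1, 0, 0, 0, 0 days, with mean 6/7 = 0.86. Over the trial, 0.857 × 92 = about 79 days, or 3.0%.
- All visits on D25: 3 × 92 = 276 days, or 10.3%.

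These are days without an open diary. They are not days on which events go unrecorded.

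**The case against.** A reader might infer that unsolicited capture as such ends on D25, and that events on D26 to D28 which did not need medical attention are never recorded. The protocol does not support that. Section 11.6 requires all AEs to be recorded to 28 days, without reference to the visit date or to the diary. The restriction to medically attended events starts at 28 days after vaccination, not at diary closure, and it turns on when the event occurred, not on when it was reported. The eCRF is a second route. Sections 9.5.1 and 9.5.2 have staff review AEs since the last visit, so a minor event on D27 mentioned at the next visit falls within the period and should be entered.

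It can also be said that the closure mark merely sits under the nominal D28 column, and that nothing states that a diary is locked early for a participant seen on D25. That is fair: early closure is the literal reading of a visit-based table, not an express rule. But no other passage gives a closing date, so nothing prevents that reading.

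What the objection does not remove is the change from prospective entry to recall. At the later visits the schedule marks SAE and AESI collection and review of ongoing AEs, while the unsolicited collection row has ended. Nothing prompts staff to ask specifically about non-attended events on D26 to D28, weeks or months afterwards.

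**Conclusion.** The point holds in a limited form. As the schedule is written, prospective diary capture of unsolicited AEs can stop on D25 (V2+25), up to 3 of 29 calendar days (10.3%) per dose before the end of the stated period, in both cohorts and after both doses. Events on the missing days remain recordable but depend on recall at a visit 24 to 143 days after closure, with the longer intervals in Cohort 2.

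The effect is small. It is nil if every visit falls on D28 or later and reaches 3 days per dose only if every visit falls on D25; the protocol does not say where practice will lie. Solicited AEs end at day 7, SAEs and AESIs are collected throughout, and medically attended AEs are recorded to the end of the study, so none of these is affected. The number of events that would be missed cannot be derived from the protocol. This is a minor inconsistency between the schedule and the recording period for a primary outcome, worth correcting because doing so costs little.

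**What to change.** Add a footnote to the closure row in Tables 2 and 3: the eDiary stays open through calendar day 28 after each dose whatever the date of the D28 or V2+28 visit, and when that visit falls earlier, staff review the remaining entries remotely once day 28 has passed. This brings the closure row into line with section 11.6 and Table 9 and reduces the diary gap from up to 3 days per dose to 0.

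The cost is a diary setting, one footnote and a brief remote check for participants seen early. No visit is added.

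The D28 and V2+28 visit windows should stay as they are. Allowing only visits on or after day 28 would also close the gap, but it would change the timing of the D28 and V2+28 blood samples, which section 6.1 uses for the secondary immunogenicity outcomes.

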#### 4.3 Schedule of procedures table: Vaccination and follow up visits (Cohort 2)

Table 3 Schedule Visit Number	1	2 2	3	4	5	6	101 ( Z) 7	8	9	10
Visit type	- Vac1	f/u	f/u	f/u	Vac2	f/u	f/u	f/u	f/u	f/u
			-	-		V2	V2	V2	V2	V2
Timeline 	D0	D1	D14	D28	V2 (D84)	+1	+14	+28	+140	+280
Time window (days)		±0	±3	±3	±14	±0	±3	±3	±28	±60
Visit Procedures										
Review contraindications, inclusion and exclusion criteria	Х				x					
Vaccination	Х				Х					
Vital signs (heart rate, temperature, blood pressure)	х	х	х	х	х	х	х	х		
Targeted medical history/physical examination, if required	(X)	(X)	(X)	(X)	(X)	(X)	(X)	(X)	(X)	(X)
Adverse Event Collection										
Solicited AE collection	D0 t	o D7			V2 to	V2+7				
Unsolicited AE collection	I	D0 to D28		V2 to V2+28						
SAEs & AESI collection	Х	Х	Х	Х	Х	Х	Х	Х	Х	Х
Review ongoing AEs		Х	х	Х	Х	Х	х	Х	Х	Х
Electronic diary (eDiary) 										
Electronic diary started	Х				Х					
Electronic diary review (in clinic)		х	Х	х		х	х	х		
Electronic diary closed				Х				х		
Urine Samples										
High sensitivity Urinary hCG ( P OCBP only)	Х				x					х
Stool samples [optional]										
Home collection of stool samples 	[X]		[X]				[X]			[X]
Blood Samples 										
HLA typing (mL)	~4									
Biochemistry, Haematology (mL) [LFTs, U+Es, FBC]	~5	~5	~5	~5	~5	~5	~5	~5	~5	~5
Immunology (mL)	~50	~30	~50	~50	~50	~30	~50	~70	~50	~50
PAXgene (ml)	~2.5	~2.5			~2.5	~2.5				
Blood volume per visit (mL)	~61.5	~37.5	~55	~55	~57.5	~37.5	~55	~75	~55	~55
Cumulative blood volume (mL)	71.5	109	164	219	276.5	314	369	444	499	554

**Table 3** Schedule of procedures: Vaccination and follow up visits (Cohort 2)

Additional unscheduled visits may occur (for example: to repeat a blood test, for additional clinical review)

REC Ref: <rec REF> IRAS project ID: 1007128 Protocol V2.0, 14th June 2023

CCHF01: A study of a new vaccine against Crimean-Congo Haemorrhagic Fever (a lifethreatening tick-borne viral disease) Page 11 of 78

eDiaries are remotely monitored in (near) real-time for the occurrence of grade  $\geq$ 3 AEs and daily for non-completion

Minor differences in blood volumes may occur depending on the collection tubes and equipment used (~ = approximately); additional repeat blood draws may be required (for example, if there is a problem with the sample, result abnormality, or participant unwell)

 optional, at the discretion of the investigator

 optional for the participant

#### 5 BACKGROUND & RATIONALE

#### 5.1 Crimean-Congo Haemorrhagic Fever (CCHF)

In 1944, an outbreak of haemorrhagic fever occurred in Russian troops re-occupying the Crimean peninsula. Cases of the disease were soon linked to tick exposure. The causative organism was identified in 1967, using suckling mice to cultivate the virus. In 1969, it was realized that the virus was the same as a virus isolated in the Belgian Congo in 1956. The disease has been referred to as Crimean-Congo haemorrhagic fever (CCHF) since the early 1970s.

The causative agent is an *Orthonairovirus* (genus *Nairoviridiae*, family *Bunyaviridales*), a negativesense, single-stranded RNA virus. The virion is spherical, approximately 80-120nm in diameter. The outer membrane is studded with two glycoproteins,  $G_N$  and  $G_C$ . The virions contain three RNA genome segments: small (S), medium (M) and large (L). A precursor for the surface glycoproteins is coded by the M segment. The S segment encodes nucleoprotein; the L segment encodes an RNA-dependent RNA polymerase.

The virus causes asymptomatic infection in many wild and domesticated vertebrates, including cattle, sheep, goats, camels and ostriches. It is usually transmitted by ixodid ticks, particularly those of the genus *Hyalomma*. The northern limit of distribution of these ticks is approximately 50°N. Transmission can also occur by contact with infected body fluids and tissues.

Human infections have been reported in numerous countries in southern Europe, the Middle East, Africa and south-west Asia. A few cases acquired by travellers from endemic countries have been diagnosed in the UK. Turkey, Iran, Russia and Uzbekistan all report more than 50 cases per year. Recently, cases have been reported in Spain. The WHO estimates that 3 billion people live in areas at risk, and that CCHF infects 10,000 to 15,000 people per year, causing 500 deaths.

Serological surveys in high-risk areas of Turkey suggest that about 88% of human infections are subclinical. In humans who develop disease, the incubation period may be from 1 to 13 days; typically, it is 1 to 5 days following a tick bite, or 5 to 7 days following exposure to infected blood or tissues. The disease is characterised by sudden onset fever, headache and myalgia; vomiting, abdominal pain and diarrhoea may also occur. A haemorrhagic phase typically begins around 3 to 5 days later. Petechial skin rashes may progress to extensive subcutaneous ecchymoses; subconjunctival and other mucosal haemorrhages may occur; there may be bleeding from the gastrointestinal and urinary tracts; cerebral haemorrhage may also occur. In fatal cases, death is usually in the second week of the illness, from haemorrhage, shock and organ failure. High viral load ( $\geq 10^8$  copies/ml) correlates with fatal outcome.

Supportive therapy, including replacement blood products, is the mainstay of treatment. Ribavirin has been observed to reduce viral load and lethality in laboratory suckling mice, but its efficacy in humans has not been definitively demonstrated in randomised clinical trials. Specific immunoglobulin therapy has been used for post-exposure prophylaxis and treatment, but efficacy has not been confirmed by case-control studies.

